4.1.1 Inclusion Criteria

Patients must meet the following criteria for study entry:

- Signed ICF
- Ages 18–55 years at time of screening
- Ability to comply with the study protocol
- Diagnosis of RMS (i.e., RRMS or aSPMS where patients still experience relapses) in accordance with the revised McDonald Criteria 2017 ([Thompson et al. 2018](#))
- At least two documented clinical relapses within the last 2 years prior to screening, or one clinical relapse in the year prior to screening (with no relapse 30 days prior to screening and at baseline)
- Patients must be neurologically stable for at least 30 days prior to randomization and baseline assessments
- EDSS score, at screening and baseline, from 0 to 5.5 inclusive
- Average T25FWT score over two trials at screening and over two trials at baseline respectively, up to 150 (inclusive) seconds
- Average 9-HPT score over four trials at screening and over four trials at baseline respectively, up to 250 (inclusive) seconds
- Documented MRI of brain with abnormalities consistent with MS at screening
- Patients requiring symptomatic treatment for MS (e.g., fampridine, cannabis) and/or physiotherapy must be treated at a stable dose during the screening period prior to the initiation of study drug on Day 1 and must have a plan to remain at a stable dose for the duration of study treatment

Patients must not initiate symptomatic treatment for MS or physiotherapy within 4 weeks of randomization.

- For females of childbearing potential: agreement to remain abstinent (refrain from heterosexual intercourse) or use adequate contraceptive methods during the treatment period and for 6 or 12 months (as applicable by the ocrelizumab [Ocrevus] local label) after the final dose of ocrelizumab.

A female is considered to be of childbearing potential if she is postmenarchal, has not reached a post-menopausal state (≥ 12 continuous months of

amenorrhea with no identified cause other than menopause), and is not permanently infertile due to surgery (i.e., removal of ovaries, fallopian tubes, and/or uterus) or another cause as determined by the investigator (e.g., Müllerian agenesis). The definition of childbearing potential may be adapted for alignment with local guidelines or regulations.

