#### **4.2.4 Supplementary Analyses**

The following supplementary analyses of the primary endpoint will be conducted according to the analysis described in Section [4.2.2](#):

1. The primary analysis will be repeated after excluding patients who meet the following exclusion criteria/do not meet the following inclusion criteria at baseline:
  - History of primary progressive MS at screening
  - Known presence of other neurological disorders that may mimic MS
  - Any concomitant disease that may require chronic treatment with systemic corticosteroids or immunosuppressants during the course of the study
  - History of or currently active primary or secondary (non-drug-related) immunodeficiency
  - Pregnant or breastfeeding

- Previous use of anti-CD20s (including ocrelizumab), unless the last infusion was more than 2 years before screening, B-cell count is normal, and the stop of the treatment was not motivated by safety reasons or lack of efficacy
- Treatment with any investigational agent within 24 weeks prior to screening (Visit 1) or five half-lives of the investigational drug (whichever is longer), or treatment with any experimental procedure for MS (e.g., treatment for chronic cerebrospinal venous insufficiency)
- Any previous treatment with mitoxantrone, cladribine, atacept, alemtuzumab, and daclizumab
- Previous treatment with fingolimod, siponimod, or ozanimod within 6 weeks of baseline
- Previous treatment with natalizumab within 4.5 months of baseline
- Previous treatment with interferons beta (1a or 1b), or glatiramer acetate within 2 weeks of baseline
- Previous treatment with any other immunomodulatory or immunosuppressive medication not already listed above without appropriate washout as described in the applicable local label (washout to be completed prior to baseline). If the washout requirements are not described in the applicable local label, then the wash out period must be five times the half-life of the medication. The pharmacodynamic (PD) effects of the previous medication must also be considered when determining the required time for washout
- Any previous treatment with bone marrow transplantation and hematopoietic stem cell transplantation
- Any previous history of transplantation or anti-rejection therapy
- Treatment with IV Ig or plasmapheresis within 12 weeks prior to randomization

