- No Diagnosis of RMS (i.e., relapsing-remitting multiple sclerosis or active secondary progressive multiple sclerosis where patients still experience relapses) in accordance with the revised McDonald Criteria 2017
- Less than two documented clinical relapses within the last 2 years prior to screening, or no clinical relapse in the year prior to screening (with no relapse 30 days prior to screening and at baseline)
- Not neurologically stable within 30 days prior to randomization and baseline assessments
- EDSS scores at screening and baseline greater than 5.5
- Average T25FWT score over two trials at screening and over two trials at baseline respectively, above 150 seconds
- Average 9-HPT score over four trials at screening and over four trials at baseline respectively, above 250 seconds

- No documented MRI of brain with abnormalities consistent with MS at screening
- Randomized to the higher dose arm and with an incorrect classification of body weight into the strata  $<75$  kg or  $\geq 75$  kg

In addition, the hypothetical strategy will be used to handle the following intercurrent events:

- Early discontinuation from study treatment
- Initiation of approved MS DMT medication
- Two consecutive missed assessments of EDSS, T25FWT and 9-HPT
- Erroneously received a quantity of ocrelizumab (including no ocrelizumab) other than the group to which the patient was randomized
- Received study drug that had been mishandled (e.g., incorrect storage temperature) and was not approved for subsequent use
- Received ocrelizumab / ocrelizumab placebo but was not randomized

Under this strategy, the data after these intercurrent events will be treated as missing and the time to onset of cCDP12 will be censored at the last assessments prior to the intercurrent event times. However, the observed data after the intercurrent events will still contribute to the confirmation period for determining if an initial progression can be confirmed. This analysis estimates the treatment effect of the higher dose of ocrelizumab in a population who always receives the study treatment as planned and without consecutive missing assessments of the primary endpoint.

2. The primary analysis will be repeated after removing the individual components from cCDP12 one at a time. This analysis will determine the extent to which the treatment effect is driven solely by each of the individual components.

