#### **4.7 CHANGES TO PROTOCOL-PLANNED ANALYSES**

Pregnancy has been added as an intercurrent event in the definition of the primary estimand in this SAP. The rationale for this change is that several pregnancies were identified after the protocol was finalized, and the presence of pregnancies can impact the interpretation of the study results.

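### Supplementary analysis 1 negates the relapse criterion with *or* where the logic needs *and*, so as written it excludes two groups of eligible patients

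*SAP*

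**What the plan says.** Protocol Section 4.1.1 gives the relapse criterion as two alternative routes: "At least two documented clinical relapses within the last 2 years prior to screening, or one clinical relapse in the year prior to screening". A bracket adds that there must be no relapse in the 30 days before screening and at baseline.

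SAP Section 4.2.4, item 1, repeats the primary analysis after "excluding patients who meet the following exclusion criteria/do not meet the following inclusion criteria at baseline". Among the listed conditions is the relapse bullet: "Less than two documented clinical relapses within the last 2 years prior to screening, or no clinical relapse in the year prior to screening". The bullet ends with the protocol's bracket, unchanged: "with no relapse 30 days prior to screening and at baseline". The bullet after it reads "Not neurologically stable within 30 days prior to randomization and baseline assessments".

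Item 1 also handles several intercurrent events by the hypothetical strategy. It says the result estimates the effect "in a population who always receives the study treatment as planned" and without consecutive missing assessments of the primary endpoint.

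**The concern.** The criterion has the form *A or B*. A patient fails it only when A and B both fail. The SAP bullet turns each half into its opposite but leaves the connective as *or*, so a patient who fails just one half is excluded even though the protocol admits that patient through the other half. The bullet and its lead-in then describe different populations: the lead-in removes only patients who miss an inclusion criterion, while the bullet also removes patients who meet it.

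The single-relapse-in-the-last-year route is one of only two ways into the trial, so the group at risk is not an edge case by construction. If the bullet is coded as written, the report would present an analysis that excludes ineligible patients when it is really an analysis of patients who meet both relapse routes.

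The bracket on the 30-day window has a related defect. It was carried over without being negated, so a relapse in that window is not stated as a reason for exclusion. The neurological-stability bullet covers this only in part: it refers to randomization and baseline, so a relapse in the 30 days before screening is not clearly caught.

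**Working it through.** **Logic.** Let *a* be the number of relapses in the year before screening and *b* the number in the year before that.

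- Protocol 4.1.1, eligible: (a + b ≥ 2) or (a ≥ 1).
- SAP bullet read literally, excluded: (a + b < 2) or (a = 0). It therefore keeps (a + b ≥ 2) and (a ≥ 1), the intersection of the two routes and not their union.
- Bullet with *and*, excluded: (a + b < 2) and (a = 0).

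| Pattern | Protocol | SAP bullet as written | Bullet with *and* |
|---|---|---|---|
| a = 0, b = 0 | ineligible | excluded | excluded |
| a = 0, b = 1 | ineligible | excluded | excluded |
| a = 0, b ≥ 2 | eligible | **excluded** | kept |
| a = 1, b = 0 | eligible | **excluded** | kept |
| a = 1, b ≥ 1 | eligible | kept | kept |
| a ≥ 2, any b | eligible | kept | kept |

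Two eligible patterns are lost under the literal reading. With *and*, the excluded patterns are exactly the ineligible ones. The result is the same whether the protocol's one relapse in the last year is read as exactly one or at least one.

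**Design figure reproduced.** SAP Section 2.2 and Protocol Section 6.1 give 205 events, 80% power, hazard ratio 0.66, two-sided 5% and 2:1 allocation. The required number of events is (1.960 + 0.842)² / [(2/9) × (ln 0.66)²] = 7.849 / (0.2222 × 0.1727) = 204.6, so 205. The design figure holds and is not in dispute.

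**Illustration of lost precision.** The documents give no distribution of *a* and *b*, so the share of patients wrongly excluded, *f*, is an assumption. With the same event rate in kept and dropped patients, D = 205 × (1 − f), SE(log HR) = 1/√(D × 2/9), and the 95% interval is exp(ln 0.66 ± 1.96 × SE):

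| f | D | SE | 95% interval |
|---|---|---|---|
| 0 | 205 | 0.148 | 0.494–0.882 |
| 10% | 184.5 | 0.156 | 0.486–0.896 |
| 30% | 143.5 | 0.177 | 0.466–0.934 |
| 50% | 102.5 | 0.210 | 0.438–0.995 |

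With *and*, f = 0 for this bullet.

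**The case against.** The strongest reply is that the lead-in already states the rule. It excludes patients who fail the inclusion criteria, the bullets only identify which criteria count, and the protocol defines this one. Discarding a whole entry route would be an implausible implementation, and a careful programmer would probably code the intended rule. That is fair, and it limits the consequence. It does not cure the text: a pre-specified population rule should not have two readings that give different analysis sets, and nothing else in the SAP corrects it.

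Other objections succeed against supporting arguments.

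- SAP Section 4.7 announces no narrowing by relapse history; its only entry is "Pregnancy has been added as an intercurrent event in the definition of the primary estimand in this SAP". But this supplementary analysis is not described in the protocol, so there was no protocol version to depart from. Nor is the section complete: it omits the move from 12-week to 24-week confirmation for the MSWS-12 endpoint. Its silence is weak evidence of intent.
- It could be argued that selection by relapse history has nothing to do with receiving treatment as planned. Other bullets in the list, such as the MRI and diagnostic criteria, are equally remote from that aim, so the argument carries little weight.
- The 205 events are the design target. SAP Section 2.3 says 205 had already been observed with the cutoff still to come, so the count at cutoff may be higher. Item 1's other exclusions and its censoring at intercurrent events pull the other way. The interval table therefore shows only how precision falls with *f*; it does not predict the result.

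The mismatch between the bullet, its lead-in and the protocol criterion does not depend on any of these.

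**Conclusion.** The concern holds, as a minor point. As written, the bullet is not the negation of the protocol criterion and removes two groups the protocol admits. This follows from the wording alone and needs no assumption.

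The practical size is unknown because the relapse-history distribution is not in the documents. The intervals above rest on an assumed *f*, equal event rates in kept and dropped patients, an estimate at the design hazard ratio, and 205 events before any other item 1 exclusion or censoring.

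Only this supplementary analysis is affected. It sits outside the hierarchy in SAP Section 2.1, and the primary analysis, event target and type I error are unchanged.

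**What to change.** - Reword the bullet so that a patient is excluded only with fewer than two documented clinical relapses in the two years before screening **and** none in the year before screening. Equivalently, state that the patient does not meet the relapse inclusion criterion of Protocol Section 4.1.1, which avoids restating it.
- List the 30-day relapse condition as its own exclusion, matching Protocol Section 4.1.1 for both screening and baseline.
- Optionally, make clear that "EDSS scores at screening and baseline greater than 5.5" means exceeding the limit at either visit. Failing the protocol's limit needs only one of the two scores to be too high, while the present wording can be read as requiring both.

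SAP version 4 was signed on 18 February 2025, after the cutoff then scheduled for December 2024. If this analysis has already been programmed, record which rule was coded. The cost is one reworded bullet and one added line, with no new data and no change to the primary analysis.

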#### **4.2.4.1 Subgroup Analyses for Primary Estimand**

The following sub-group analyses will be performed via change in the population attribute of the primary estimand:

- Age at screening ( $\leq 45$  vs.  $> 45$  years)
- EDSS ( $< 4.0$  vs.  $\geq 4.0$ )
- Region (United States vs. ROW)
- Weight at Baseline ( $< 75$  vs.  $\geq 75$  kg)
- Presence or absence of T1Gd + lesions at baseline
- Duration since MS symptoms onset at baseline ( $< 3$  years,  $\geq 3$  to  $\leq 10$  years,  $> 10$  years)
- BMI at baseline ( $< 30$  vs.  $\geq 30$  kg/m^2)
- Prior DMT at baseline (yes vs. no)
- Duration since MS onset and disability level at baseline ( $< 3$  years & EDSS  $< 2$ ,  $< 3$  years & EDSS  $\geq 2$ ,  $\geq 3$  years & EDSS  $< 2$ ,  $\geq 3$  years and EDSS  $\geq 2$ )

All results will be summarized in a forest plot.

### **4.3 SECONDARY ESTIMANDS AND ANALYSES**

Hypothesis tests for the secondary estimands as well as the hierarchical order in which they will be tested are described in Section 2.1. The p-value is interpreted as confirmatory if the primary estimand and each preceding estimand have reached the significance level of 0.05, otherwise it is reported as non-confirmatory.

All attributes for the secondary estimands are provided in Table 1. Further details on the estimands attributes and estimation methods (i.e., estimators) are provided below.

#### **4.3.1 Estimands for Time to Event Endpoints**

All secondary estimands which focus on the analysis of time to event endpoints have the same estimand attributes (except for Endpoint attribute) and estimation method as for the primary estimand (Section 4.2.2). Details on the definition of the secondary time to

event endpoints are provided in [Table 1](#) and [Section 4.2.1](#). Further details on the definition of the secondary time to event endpoints are provided below.

The following time to event secondary endpoints will be analyzed:

- Time to onset of cCDP24
- Time to onset of CIT25FWT12
- Time to onset of 12-week composite confirmed disability progression independent of protocol-defined relapses (cPIRA12)
- Time to onset of CDP12
- Time to onset of cCDP48
- Time to onset of CWSDMT12
- Time to onset of CIMSWS24

The time to onset of CIT25FWT12, cPIRA12, CDP12, CWSDMT12 will be defined over a 12-week confirmation window ( $\geq 84$  days) for the disability progression. The conditions for the confirmation of the disability progression described for the primary estimand in [Section 4.2.1](#) will also be applied to these endpoints.

For the disability progression the time to onset of cCDP24 and CIMSWS24 will be defined over a 24-week confirmation window ( $\geq 161$  days) and the time to onset of cCDP48 will be defined over a 48-week confirmation window ( $\geq 329$  days).

Time to onset of the individual components of cCDP12 (CDP12, CIT25FWT12 and CI9-HPT12) independent of protocol defined relapses is defined similarly to time to onset of the individual components of cCDP12, except that two additional conditions must be satisfied:

- The baseline reference assessment (EDSS, T25FWT, or 9-HPT values) is re-baselined at the first assessment  $\geq 30$  days after the onset of each protocol-defined relapse. Furthermore, the re-baselined disability assessment is set equal to the maximum of the disability status at the new re-baselined assessment and the previous re-baselined assessment.
- No protocol-defined relapse should occur between baseline reference assessments and within 30 days after initial progression, and 30 days prior to and after the confirmation visit.

The definitions of disability progression independent of relapses and relapse associated worsening are cited in Kappos et al. ([2020](#)).

The SDMT is a brief and easy to administer performance test that involves a simple substitution task. Using a reference key, the examinee has 90 seconds to pair specific numbers with given geometric figures. In this study, responses will be collected orally.

The 12-Item Multiple Sclerosis Walking Scale (MSWS-12) is a self-report measure of the impact of MS on the individual's walking ability.

#### 4.3.2 Estimand for Annual Rate of Percent Change from Baseline in Total Brain Volume

**Estimand:** The estimand is the mean difference in annual rate of percent change from baseline in total brain volume between the higher and approved dose of ocrelizumab arms in patients with RMS where no treatment discontinuation nor initiation of alternative MS treatment can occur, according to the following attributes:

**Estimator:** A random coefficient regression model (RCRM) will be used to quantify mean difference in annual rate of percent change from baseline in total brain volume between the higher and approved dose of ocrelizumab arms. The mean structure of the model is as follows:

$$E[Y_{ij}|time_{ij}, T_i, X_i] = time_{ij}(\beta_0 + \alpha X_i + \beta_1 T_i + u_i),$$

where  $Y_{ij}$  represents percentage change in total brain volume from baseline at visit  $j$  for patient  $i$ ,  $time_{ij}$  is the time from baseline in years at visit  $j$  for patient  $i$ ,  $T_i$  is an indicator such that  $T_i = 1$  if patient  $i$  was randomized to the higher dose of ocrelizumab arm and  $T_i = 0$  otherwise,  $X_i$  is a vector containing the cube root of the baseline total brain volume and randomization stratification factors for patient  $i$ ,  $\alpha$  is a vector of regression coefficients for  $X_i$ ,  $\beta_0$  is the adjusted mean of the annualized rate of percentage change in total brain volume for the approved dose of ocrelizumab arm,  $\beta_1$  is the adjusted mean difference in the annualized rate of percentage change in total brain volume between the higher and approved dose of ocrelizumab arms, and  $u_i$  is a subject-specific random effect that follows a mean zero normal distribution. The statistical significance of the estimated mean difference will be calculated by using the Wald test, where the standard error is estimated using the robust sandwich variance estimator.

In order to estimate the aforementioned estimand, the following **intercurrent event** handling strategies will be applied:

**Early discontinuation from study treatment:** All data after treatment discontinuation will be treated as missing following the hypothetical strategy.

**Initiation of an approved MS DMT medication:** All data after treatment discontinuation will be treated as missing following the hypothetical strategy.

**Pregnancy:** All data pre and post pregnancy onset will be included in the analysis following treatment-policy strategy.

**Death:** This is anticipated to be very rare, but in case of occurrence, it will be handled with the hypothetical strategy. That is, data after death will be treated as missing.

Missing data resulting from patients that withdraw their consent to participate in the study and/or a serious GCP breach will not be imputed.

Sample Statistical Analysis System code can be found below (Statistical Analysis System code is regarded as “draft” until fully validated at the analysis stage):

```
PROC MIXED DATA=dataset empirical;  
CLASS USUBJID ARMCD StratificationFactors;  
MODEL AVAL_N = ARMCD Baseline StratificationFactors / solution cl;  
RANDOM intercept / subject=USUBJID type=un;  
run;
```

where AVAL\_N is the percentage change in brain volume divided by time at each scheduled visit, and Baseline is the cube root of total brain volume at baseline.

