4.4.3 Prohibited Therapy and Alternative Treatment Post-Ocrelizumab

The following therapies for MS are not permitted while under study treatment: B-cell targeted therapies (e.g., rituximab, atacept, belimumab, ofatumumab, or others), natalizumab, fingolimod, siponimod, alemtuzumab, daclizumab, cladribine, teriflunomide, dimethyl fumarate, interferons, glatiramer acetate, cyclophosphamide, mitoxantrone, azathioprine, mycophenolate mofetil, cyclosporine, methotrexate, total body irradiation, bone marrow transplantation, IV Ig, plasmapheresis, other approved or investigational therapies for MS.

After patients have completed (or discontinued) treatment with ocrelizumab, they may receive alternative treatment for their MS as judged clinically appropriate by the investigator. If patient prematurely discontinues the randomized treatment and starts an approved MS DMT medication, they will continue to be followed up in DBT phase until primary analysis (please refer to Section 3.1.1.2). However, as sufficient data are not available regarding risks associated with switching to other products, the following recommendations are given:

- Caution is advised while patients remain B-cell depleted.
- Because of the unknown safety risk of administering disease-modifying treatments for MS after discontinuation of ocrelizumab, certain treatments for MS, such as lymphocyte-depleting agents or lymphocyte-trafficking blockers (alemtuzumab, natalizumab, fingolimod, dimethyl fumarate, cyclophosphamide, azathioprine, cladribine, daclizumab, etc.) are strongly discouraged for as long as the patient remains B-cell depleted because of unknown effects on the immune system (e.g., increased risk, incidence, or severity of infection).

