6.4 EFFICACY ANALYSES

The analysis population for the efficacy analyses will consist of all randomized patients, with patients grouped according to their assigned treatment.

For analysis purposes, treatment discontinuation will be defined as 24 weeks after the last dose.

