6.4.2 Secondary Efficacy Endpoints

The secondary efficacy objective is *twofold*. *First*, to demonstrate superiority of a higher dose of ocrelizumab over the approved dose of ocrelizumab on the basis of the endpoints listed in Section 2.1.2. *Second*, to demonstrate that both the higher dose and standard dose of ocrelizumab can lead to a significant reduction in NfL from baseline on the basis of the endpoints listed in Section 2.1.2

Secondary estimands: For all time to event endpoints, the comparison of interest is the difference in time to event between treatment arms, as expressed by the hazard ratio.

For all other endpoints, *with the exception of the NfL endpoints*, the comparison of interest is the difference in variable means between treatment arms. *For the NfL endpoints, the comparisons are the change from baseline at Week 48 within each treatment arm.*

All comparisons, except for the MRI *and* NfL endpoints (*e.g.*, the change in brain volume), will be made regardless of adherence to the randomized treatment or use of an approved MS DMT medication (treatment-policy strategy). For the MRI *and* NfL endpoints, the comparison will be made as if no treatment discontinuation or switch to an approved MS DMT medication has occurred (hypothetical strategy).

If primary estimand is statistically significant, all secondary estimands will be tested in a fixed sequence at 0.05 significance level. The sequence of hierarchical testing will be specified in the SAP.

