## **4. STATISTICAL ANALYSES**

### **4.1 GENERAL CONSIDERATIONS**

All statistical hypotheses for the primary and secondary endpoints and treatment comparisons will be tested at the 5% significance level ( $\alpha=0.05$ ) against two-sided alternatives.

All primary and secondary efficacy endpoints will be stratified by region, age at screening, baseline EDSS and baseline body weight for analysis. The regional stratifications are United States and ROW. The age categories are  $\leq 45$  years and  $> 45$  years. The EDSS categories are  $< 4.0$  and  $\geq 4.0$ . The body weight categories are  $< 75$  kg and  $\geq 75$  kg.

The baseline for the primary endpoint is the date of randomization. The baseline value of the endpoint, e.g., EDSS, T25FWT and 9-HPT values, is the most recent value up to and including the date of randomization but before first infusion of study drug. A subject with delayed dosing may receive the first dose 2 weeks after the baseline visit; if an EDSS, T25FW or 9-HPT score is recorded between the randomization date and the date of the first dose, this value will be considered as a post-baseline assessment.

FAS will be used in the analysis of the primary and secondary estimands, and exploratory efficacy endpoints. Safety analysis set (SAS) will be used to summarize safety data. For analysis purposes, the time of treatment discontinuation will be defined as 24 weeks after the last dose prior to the date of treatment discontinuation recorded in the electronic Case Report Form (eCRF).

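### For brain volume and NfL, the SAP's rule for starting another DMT removes no data when that DMT starts before last dose plus 24 weeks

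*SAP*

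**What the plan says.** For total brain volume, SAP 4.3.2 defines the target as a setting "where no treatment discontinuation nor initiation of alternative MS treatment can occur". SAP 4.3.3 sets the same condition for NfL at Week 48. SAP Table 1 lists early discontinuation and DMT initiation separately for both endpoints and assigns the hypothetical strategy to each. Protocol 6.4.2 likewise names a switch to another DMT alongside discontinuation for the MRI and NfL endpoints.

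The handling text then gives one sentence for both events, in 4.3.2 and again in 4.3.3: "All data after treatment discontinuation will be treated as missing following the hypothetical strategy".

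The date meant by discontinuation is fixed in SAP 4.1: "the time of treatment discontinuation will be defined as 24 weeks after the last dose prior to the date of treatment discontinuation recorded" in the eCRF. Protocol 6.4 agrees: "For analysis purposes, treatment discontinuation will be defined as 24 weeks after the last dose".

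On when another DMT may begin, Protocol 4.4.3 does not permit other MS therapies under study treatment. Once ocrelizumab is completed or discontinued, "they may receive alternative treatment for their MS as judged clinically appropriate by the investigator". No 24-week wait is stated. Protocol 3.1.1.2 keeps such patients in the double-blind phase with efficacy follow-up, so measurements on the new DMT are collected.

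**The concern.** The DMT-initiation entry has no effect of its own, because the start of a new DMT never triggers removal of data. Between that start and the analysis-defined discontinuation date, a patient's NfL and MRI values count as ocrelizumab values although the estimand excludes alternative treatment.

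Three tests in the hierarchy of SAP 2.1 use this rule: NfL in the higher-dose arm (fourth), NfL in the approved-dose arm (fifth) and brain volume (tenth). NfL is tested within each arm by a separate model, so a shift in one arm is not offset by a comparison with the other. SAP 4.4.3 (thalamic volume, black-hole radius, spinal cord volume) and 4.4.5 (lesion counts) adopt the brain-volume handling by reference.

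**Working it through.** The plan gives no figure to reproduce here. The check sets the rule against the visit calendar.

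**Inputs**
- Cutoff = last dose + 24 weeks (SAP 4.1, Protocol 6.4).
- Doses at Weeks 0 and 2 (split first dose), then every 24 weeks (Protocol 3.1, Table 1).
- NfL visits in the model: Weeks 12, 24 and 48 (SAP 4.3.3).
- MRI at Weeks 24, 48 and 120, then every 48 weeks (Protocol Appendix 1).

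**Condition for keeping an on-DMT value:** DMT start < assessment date ≤ last dose + 24 weeks.

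**Result at nominal visit weeks, for a DMT start inside the gap**

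| Last dose (week) | Cutoff (week) | NfL that can be kept on DMT | MRI that can be kept on DMT |
|---|---|---|---|
| 0 | 24 | Weeks 12, 24 | Week 24 |
| 2 | 26 | Weeks 12, 24 | Week 24 |
| 24 | 48 | Week 48 | Week 48 |
| 48 | 72 | none | none |
| 72 | 96 | none | none |
| 96 | 120 | none | Week 120 |

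Week 12 NfL is affected only if the DMT started before it. The pattern continues on the later MRI schedule: a last dose at Week 144 gives a cutoff at Week 144 + 24 = 168, which is the next scan after Week 120 (120 + 48 = 168).

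**Example.** Last dose at Week 24, with an assumed DMT start at Week 28, 32, 36 or 44. The Week 48 values are then taken 48 − 28 = 20, 16, 12 or 4 weeks into the new DMT. The current rule keeps them if they are taken by Week 48. A rule that cuts at DMT start drops them.

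**Boundary.** When dosing is on schedule, Weeks 24, 48 and 120 fall on the cutoff itself (Week 24 falls inside it when the last infusion was at Week 2). Dosing visits have a window of ±5 days and MRI ±4 weeks, so the actual dates decide. A value after the cutoff is already removed.

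**No recorded discontinuation.** SAP 4.1 counts from the last dose before the eCRF discontinuation date. With no such date there is no cutoff, and a DMT start removes nothing.

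**Possible effect on NfL (assumed inputs).** NfL is analysed on the log scale. If a fraction f of an arm keeps an on-DMT Week 48 value that is r times its hypothetical value, the arm's geometric mean ratio is multiplied by about r^f.
- f = 0.01: 0.8^0.01 = 0.998; 1.5^0.01 = 1.004.
- f = 0.05: 0.8^0.05 = 0.989; 1.5^0.05 = 1.020.

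The documents support neither f nor r. With f = 0 the factor is 1.

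**Comparison within the SAP.** The primary-estimand text (4.2.2) and the relapse-rate text (4.4.6) tie the DMT entry to initiation of the alternative treatment. Supplementary analysis 1 (4.2.4) applies the hypothetical strategy to the primary endpoint by discarding data after each listed intercurrent event, DMT initiation included. Only the 4.3.2 and 4.3.3 wording refers back to discontinuation.

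**The case against.** The best defence is that a recorded stop should precede any switch, because other DMTs are not permitted under study treatment, so a cut at discontinuation would cover the switch. That would hold if discontinuation meant the eCRF date. SAP 4.1 and Protocol 6.4 define it as last dose plus 24 weeks, so the gap remains.

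A second defence is that the intent is plain. Table 1, both estimand statements, Protocol 6.4.2 and supplementary analysis 1 all point to removal at DMT start, so this looks like a copying slip. That is probably right, but the handling text is what a programmer would implement.

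The defence is strongest on size, and there it stands:
- The gap is at most one dosing interval. A reader might infer that on-DMT data are kept generally, but for any DMT started after last dose plus 24 weeks they are all already removed.
- Protocol 4.4.3 strongly discourages certain DMTs while B cells are depleted. Section 5.1.1.1.6 reports a median repletion time of 72 weeks (range 27–175) in the 600 mg group of the Phase II study. The shortest of these exceeds 24 weeks, so that advice spans the whole gap, though it does not cover every DMT.
- Brain volume is a slope over all available scans, so one retained scan is one of several points. Only NfL is tested at a single exposed visit.

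A reader might also infer a count: 865 × 0.05 × 24/52 ≈ 20 patients stopping per interval, of whom 25–75% switch early, giving 5–15 contaminated values. The documents do not support it. The 5% is the annual dropout rate assumed for sample size, not a treatment-stopping rate, and no early-switch share is given. The count also makes no allowance for values falling after the cutoff.

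**Conclusion.** The mismatch between estimand and handling rule is certain on the text of SAP 4.3.2, 4.3.3 and 4.1. It is confined to DMT starts before last dose plus 24 weeks, or without a recorded discontinuation, and to the few assessments in the table and later 48-weekly scans on the same pattern.

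The number affected is unknown, plausibly from near zero to a handful. Under the assumed 1–5% of an arm and on-DMT to hypothetical NfL ratios of 0.8–1.5, the arm's geometric mean ratio moves by a factor of about 0.989 to 1.020. It would be tempting to conclude that three confirmatory tests are compromised. The documents do not show that, since no change in any result is demonstrated. The correction is still worth making, because these tests belong to the formal hierarchy and their data rule should match the estimand.

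**What to change.** Under DMT initiation in SAP 4.3.2 and 4.3.3, replace the repeated sentence with: *All data after the earlier of the date of DMT initiation and the treatment discontinuation time defined in Section 4.1 will be treated as missing.* Sections 4.4.3 and 4.4.5 inherit the correction. State also that the DMT date applies when no discontinuation is recorded.

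No new data should be needed. Concomitant medication is recorded in the eCRF (Protocol 4.4), supplementary analysis 1 already relies on the DMT start time, and SAP 4.6.1 already plans a table of switchers. The cost is a few lost measurements, which the models then treat as missing. If the data are already unblinded, record the change as a clarification and report the results under both rules.
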